7.2.4 Measurements of Exposure and Treatment Compliance

Exposure

Exposure will be presented by displaying Individual Study Duration, Number of Drops Single Dose Scheme in Study Eye/Non-Study Eye, Number of Drops Multiple Dose Scheme in Study Eye/Non-Study Eye, which will be derived as follows

- Individual Study Duration:
Date of Study Discontinuation/Completion (as recorded on eCRF Page “End of Study”) – Date of Informed Consent (as recorded on eCRF Page “Informed Consent”) + 1.
- Number of Drops Single Dose Scheme in Study Eye:
Number of records on eCRF Page “Administration of Study Drug” at D1 Visit, which are indicating an administration of study medication in the study eye according to the assigned randomization number documented on the eCRF Page “Randomization”; 0 if no administration is indicated (i.e. no data record found or box ‘Not Done’ is ticked). For the single dose scheme only 1 drop should be applied according to the protocol.
- Number of Drops Single Dose Scheme in Non-Study Eye:
Number of records on eCRF Page “Administration of Study Drug” at D1 Visit, which are indicating an administration of study medication in the non-study eye according to the assigned randomization number documented on the eCRF Page “Randomization”; 0 if no administration is indicated (i.e. no data record found or box ‘Not Done’ is ticked). For the single dose scheme 1 drop should be given according to the protocol.
- Number of Drops Multiple Dose Scheme in Study Eye:
Number of records on all eCRF pages “Administration of Study Drug” at D2, D3, D4, D5, D6 visits, which are indicating an administration of study medication in the study eye according to the assigned randomization number documented on the eCRF Page “Randomization”; 0 if no administration is indicated at all visits (i.e. no data record found or box ‘Not Done’ is ticked). For the multiple dose scheme, 30 drops should be given according to the protocol.
- Number of Drops Multiple Dose Scheme in Non-Study Eye:

Number of records on all eCRF pages “Administration of Study Drug” at D2, D3, D4, D5, D6 visits, which are indicating an administration of study medication in the non-study eye according to the assigned randomization number documented on the eCRF Page “Randomization”; 0 if no administration is indicated at all visits (i.e. no data record found or box ‘Not Done’ is ticked). For the multiple dose scheme, 30 drops should be given according to the protocol.

Compliance

For the evaluation of compliance, the following derivations will be created:

- Compliance Single Dose Scheme in Study Eye (%):
is defined as $100 \times \text{Number of Drops Single Dose Scheme in Study Eye}$.
- Compliance Single Dose Scheme in Non-Study Eye (%):
is defined as $100 \times \text{Number of Drops Single Dose Scheme in Non-Study Eye}$.
- Compliance Multiple Dose Scheme in Study Eye (%):
is defined as $100 \times \text{Number of Drops Multiple Dose Scheme in Study Eye} / 30$.
- Compliance Multiple Dose Scheme in Non-Study Eye (%):
is defined as $100 \times \text{Number of Drops Multiple Dose Scheme in Non-Study Eye} / 30$.

For the analysis, the proportion of 100% compliant subjects will be presented per aspect based on these derivations.

7.2.5 Study Medication

Table 3: Study Treatments shows the study treatments and how they will be labelled in all TLF outputs.

Table 3: Study Treatments

Treatment arm label	Associated Treatment
rhNGF	rhNGF 20 µg/m: single drop on D1, one drop six times a day on D2, D3, D4, D5, D6
Vehicle	Vehicle control: single drop on D1, one drop six times a day on D2, D3, D4, D5, D6

7.2.6 Primary Safety Endpoints

For this study, the incidence of the following events will serve as primary safety endpoints:

- Treatment emergent adverse events (TEAEs) as defined in section 7.2.8.
- TEAEs during single dose scheme (TEAEs Single Dose):
these comprise all TEAEs, which start after first dose of study treatment and before the date/time of administration of the first dose at Treatment Day 2. In case of missing time, a TEAEs with a start date of the day of D1 Visit will be considered as TEAEs Single Dose.
- TEAEs during multiple dose scheme (TEAEs Multiple Dose):
these comprise all TEAEs during the treatment period, which start after the date/time of first dose of study treatment at D2 Visit. In case of missing time, a TEAEs with a start date on the day of D2 up to D6 Visit will be considered as TEAEs Multiple Dose.

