10 STATISTICS

10.1 Study endpoints

Primary safety endpoints are:

- Incidence of treatment emergent adverse events (TEAEs).
TEAEs are defined as an adverse event (AE), which start after first dose of study treatment. These comprise AEs during the treatment and follow-up period.
- Incidence of treatment emergent adverse events during 1st dose schedule (TEAEs Dose 1).
TEAEs Dose 1 are defined as TEAEs, which start after first dose of study treatment and before administration of the first dose at Treatment Day 2.
- Incidence of treatment emergent adverse events during 2nd dose schedule (TEAEs Dose 2).
TEAEs Dose 2 are defined as TEAEs, which start on/after the first dose at Treatment Day 2 and before Follow Up Day 7 (FU1) visit.

Secondary safety endpoints are:

- Incidence of Follow-Up AEs (FUAE)
FUAEs are defined as TEAEs which start on or after Follow Up Day 7 (FU1) visit visit.
- Incidence of ocular TEAEs by eyes.
- Course of ECG parameters ventricular rate, PR interval, QRS duration and QT interval over all visits.
- Course of vital signs parameters systolic and diastolic blood pressure, pulse rate, respiratory rate and body temperature over all visits.
- Changes from baseline in biochemistry parameters over all visits.
Baseline is defined as the Laboratory assessment of Baseline (D-1) Visit
- Changes from baseline in hematology parameters over all visits.
Baseline is defined as the Laboratory assessment of Baseline (D-1) Visit
- Shift in overall interpretation of urinalysis over all visits. Laboratory assessment at Baseline (D-1) Visit is considered as reference for assessing the shift.
- Course of intraocular pressure by eye over all visits.
- Course of visual acuity score by eyes over all visits
The visual acuity score will be derived as the total numbers of letters, which were read correctly at 4 meter plus the total number of letters read at 1 meter as collected on the eCRF page. When 20 or more letters are read at 4 meters the visual acuity score for that eye is recorded as the number of letters correct at 4 meters plus 30. The subject gets credit for the 30 letters at 1 meter even though they did not have to read them. If no letters are read correctly at either 4.0 meters or 1 meter, then the visual acuity score is recorded as "0."
- Course of LogMAR by eyes over all visits.
The logMAR will be derived as – log (Snellen Equivalent result)
- Course of TFBUT by eye over all visits.

- Course of overall NEI score by eye over all visits.

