3.6 Changes in the Conduct of Study or Planned Analysis compared to Protocol

The following changes of the study conduct did affect the planned analysis:

- Study protocol section 8.2 describes the assessment of “daily consumption of caffeine”. This was not collected on the eCRF and is therefore not presented in the analysis.
- Study protocol section 8.2 describes the assessment of “daily consumption of alcohol”. However, assessment of usual alcohol consumption was changed to weekly assessment to facilitate verification of exclusion criterion 7.
- Study protocol section 7 describes the assessment of body weight for all scheduled assessment times of vital sign. However, body weight was assessed on the eCRF only at Screening Visit. As a consequence, no presentation of post-baseline body weight will be provided.
- No clinical interpretation are recorded for urinalysis including the endpoint “overall interpretation of urinalysis results”. As a consequence, this endpoint will not be analyzed.
- In the study protocol section 8.2, assessment of the horizontal diameter of the cornea is specified as part of the slit lamp evaluation. However, this was not collected in the eCRF and is therefore not part of the analysis.
- For Fundus Ophthalmology, the site did perform additional unscheduled assessments in a non-dilated manner at D1 8hr and D2 pre-dose. These assessments were done without any specific safety reason, so results were not entered in the eCRF as unscheduled assessments and are therefore not included in the data listings.

The following refinements of the pre-planned analysis in the study protocol were implemented in this SAP:

- For a better perceivability, the primary safety endpoints are rephrased to Incidence of Treatment Emergent Adverse Events during Single/Multiple Dose Scheme, respectively.
- In the eCRF, no start time of Adverse Event has been recorded. During SAP creation, this was considered as required for a precise assignment of AEs to Single-Dose or Multiple Dose Scheme. and multiple dose treatment phase. As a consequence, the start times of an AE was entered in the eCRF as free-text comment associated to the AE start date field.
- Fundus Ophthalmology was performed in a dilated manner at Screening Visit, whereas a non-dilated Fundus Ophthalmological assessment was done for all other study visits. As a consequence, data listings will clearly indicate the mode of fundus ophthalmological assessments.

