7.1 Definition of Time Points

The study consists of 12 scheduled clinical evaluation visits as described in Table 2.

The **Date of First Study Treatment** will be identified as the (earliest) date documented on the eCRF page “Administration of Study Drug” at D1 Visit, irrespective of the applied eye.

The **Treatment Day** of an event/assessment will be calculated relative to the First Study Treatment.

The Treatment Day of events/assessments occurring before the First Study Treatment will be calculated as:

- Treatment Day = (Date of assessment/event - Date of First Study Treatment).

For events/assessments occurring on or after First Study Treatment Administration, Treatment Day will be calculated as:

- Treatment Day = (Date of assessment/event - Date of First Study Treatment) + 1.

Relative Assessment Time of assessments is derived as the difference of the 24hr clock time on a respective day minus the time of the First Study Treatment at D1 Visit in hours utilizing 1 decimal. For example, if the time of First Study Treatment at D1 Visit was on 8:00 hr and the time of Baseline 0.5 hour was on 8:30 hr, then the Relative Assessment time will be 0.5 hours. So, the Relative Assessment Time is presenting the relative time within a visit day.

Relative Treatment Time Single Dose Scheme (hr) will be derived for all PK assessments and is defined as difference of the Date/Time of the assessment minus the time of First Study Treatment at D1 Visit in hours utilizing 1 decimal. For example, if the time of First Study Treatment at D1 Visit was on 8:00 hr and the time of D2 Pre-Dose was on 07:00 hr on the next day, then the Relative Treatment Time Single Dose Scheme will be 23.0 hours. So, the Relative Treatment time Single Dose Scheme presents the Time to First Study Treatment.

Relative Treatment Time Multiple Dose Scheme (hr) will be derived for all assessments on or after D2 and is defined as difference of the Date/Time of the assessment minus the time of First Study Treatment at D2 Visit in hours utilizing 1 decimal. For example, if the time of First Study Treatment at D2 Visit was on 8:00 hr and the time of D3 Pre-Dose was on 07:00 hr on the next day, then the Relative Treatment Time Single Dose Scheme will be 23.0 hours. So, the Relative Treatment time Multiple Dose Scheme presents the Time to First Study Treatment of the Multiple Dose Scheme.

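### SAP 7.2.6 and 7.2.8 do not reproduce the dose-scheme adverse-event windows of protocol 10.1, SAP 3.4 and SAP 7.1, so a few boundary events are left unassigned or assigned differently

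*SAP*

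**What the plan says.** Protocol 10.1 (Study endpoints) sets the frame. On onset it says "TEAEs are defined as an adverse event (AE), which start after first dose of study treatment". Events of the second dose schedule are those "which start on/after the first dose at Treatment Day 2 and before Follow Up Day 7 (FU1) visit". The first schedule ends before that Day 2 dose, and follow-up events begin with the FU1 visit. SAP 3.4 repeats these definitions. SAP 7.1 agrees at both the D2 and the D7 cut: the multiple-dose period begins with the first D2 intake, and the treatment period closes just before the first D7 assessment.

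SAP 7.2.6 restates the two dose-scheme endpoints. Single-dose events are those "which start after first dose of study treatment and before the date/time of administration of the first dose at Treatment Day 2". For multiple-dose events, "these comprise all TEAEs during the treatment period, which start after the date/time of first dose of study treatment at D2 Visit". If the time is missing, "a TEAEs with a start date on the day of D2 up to D6 Visit will be considered as TEAEs Multiple Dose".

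SAP 7.2.8 takes the period from an eCRF question with three answers (before treatment, during treatment, follow-up) and uses the onset date only if that question is blank. Its date definitions count as TEAE anything from the calendar date of first treatment, close the treatment period with the D6 visit, and make a start date from the D7 visit onward a follow-up event (FUAE). Non-TEAE is defined differently, by the first administration. An event that cannot be classified is placed in the treatment period.

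SAP 3.6 says "For a better perceivability, the primary safety endpoints are rephrased to Incidence of Treatment Emergent Adverse Events during Single/Multiple Dose Scheme". It also reports that start times were judged necessary for assigning events to a scheme, so "the start times of an AE was entered in the eCRF as free-text comment associated to the AE start date field". It lists no change of window.

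**The concern.** Two of the three primary safety endpoints depend on these cuts, and each has its own table (14.2-04.1 and 14.2-05.1) besides the summary in 14.2-01.1. Single-dose, multiple-dose and follow-up windows should cover every TEAE once. If the operative definitions in 7.2.6 and 7.2.8 differ from those in the protocol, an event can drop out of both dose schemes or move from a primary to a secondary endpoint.

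The D2 tie is not far-fetched. Dose times are recorded (protocol 5.4.2), AE start times were added to the eCRF, and a reaction on instillation could carry the time of the dose. Quality control under SAP 5.3 compares output with the SAP, so a program that follows 7.2.6 to the letter would pass with the gap in place.

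**Working it through.** The plan gives no figure to reproduce. The check runs boundary events through each definition and then sizes the result.

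**1. Event timed at the first D2 dose**

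| Source | Assignment |
|---|---|
| Protocol 10.1, SAP 3.4 (*on/after*) | Multiple dose |
| SAP 7.1 (period begins with that intake) | Multiple dose |
| SAP 7.2.6, time recorded (*before* / *after*) | Neither scheme |
| SAP 7.2.6, time missing | Multiple dose |

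One minute earlier the event is single dose, and one minute later multiple dose, under SAP 3.4, 7.1 and 7.2.6 alike. The gap is the tie alone. Recording the time removes an event that would count if the time were absent. The eCRF period answer cannot settle it, because both schemes lie within the treatment answer.

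**2. Event on D7 at 03:00, before FU1**

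| Source | Assignment |
|---|---|
| Protocol 10.1, SAP 3.4, SAP 7.1 | Multiple dose |
| SAP 7.2.8 date wording | FUAE |

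SAP 7.2.6 limits multiple-dose events to the treatment period, so its upper end depends on whether 7.1 or 7.2.8 supplies that period.

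**3. Event on D1 before the first dose.** Protocol 10.1: not a TEAE. SAP 7.2.8: a non-TEAE (before the first administration) and also a TEAE (on the date of first treatment).

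**4. Event with no start date.** If the period question is also blank, 7.2.8 defaults it to a TEAE in the treatment period. The fallback in 7.2.6 covers a missing time on a known date only, so the event has no dose scheme. The 7.2.8 date imputation does not help: it serves relative days only and leaves a completely missing date alone.

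**Size in subjects.** Planned groups are 20 rhNGF and 10 vehicle (protocol 10.2). One reassigned subject with no other event in the window changes incidence by 1/20 = 5 points or 1/10 = 10 points.

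**Size in time, item 2.** Protocol Appendix 3 puts the first D2 dose at hour 24, the last D6 dose at hour 130 and FU1 at hour 144.
- Multiple-dose window: 144 − 24 = 120 h.
- The disputed span runs from midnight to FU1. SAP 7.1 uses an illustrative clock, "if the time of First Study Treatment at D1 Visit was on 8:00 hr". With FU1 at 08:00 the span is 8 h, and 8/120 = 6.7%.
- With FU1 assumed between 06:00 and 10:00 it is 6 to 10 h: 6/120 = 5.0% to 10/120 = 8.3%.
- At 08:00, midnight is hour 144 − 8 = 136, so the span lies 136 − 130 = 6 h to 144 − 130 = 14 h after the last nominal dose.

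These are clock hours, not expected shares of events.

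**The case against.** The best defence is that the right windows are already in SAP 3.4 and 7.1, that the eCRF answer decides the period first, and that little hangs on the rest. Much of this stands. Items 2 and 3 act only where the period answer is blank or disagrees with 7.1. No inferential analysis is planned (SAP 8.2), and all adverse events are listed (SAP 10.6.1). The defence does not reach item 1, which the period answer cannot resolve.

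Four stronger readings are tempting, and the documents do not support them.

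- A reader might infer that most boundary events are lost or counted twice. A D1 pre-dose event also meets the non-TEAE definition, and belonging to no scheme is then correct. An event timed exactly at the D1 dose is already excluded by the protocol's own *after*. The D7 event falls in two categories only if 7.1 is used for one and 7.2.8 for the other; the conflict is over which section governs.
- A reader might infer that a D7 event with missing time has no rule. The 7.2.8 date wording makes it an FUAE, and the 7.2.6 fallback stops at D6.
- A reader might infer that nothing reconciles period answers with dates. Protocol 12.2 provides for edit checks, SAP 5.1 refers to data management and validation plans, and SAP 8.3.3 requires a clean database and points to a separate blind data review plan. The scope listed in 8.3.3 names only sight-threatening events among AE items, but those other plans are not available here and may hold such checks.
- A reader might infer that 3.6 conceals a deliberate change of window. Its rephrasing most naturally concerns the endpoint labels.

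**Conclusion.** The inconsistency is real and minor. As written, 7.2.6 leaves a TEAE timed at the first D2 dose out of both dose-scheme endpoints. The 7.2.8 wording conflicts with protocol 10.1 for D7 events before FU1 and for D1 pre-dose events, and an event with no start date has no scheme. Overall TEAE incidence can change only through the D1 item.

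The 5- and 10-point shifts assume the planned group sizes and a subject with no other event in the window. The D7 span rests on an assumed FU1 clock time. How often any of these events would occur cannot be learned from the documents; exact ties and missing dates should be rare in subjects resident at the clinic.

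**What to change.** Before unmasking:

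1. In SAP 7.2.6, define multiple dose as onset at or after the date and time of the first D2 dose and before the first FU1 assessment. Single dose keeps its end before that dose.
2. In SAP 7.2.8, end the treatment period just before the first FU1 assessment and start FUAEs from it. Keep D7 events with missing time as FUAEs, or state another rule.
3. Define TEAE by date and time after the first D1 dose, as in protocol 10.1. If the sponsor wants a different rule, including for an event at the exact D1 dose time, declare it in SAP 3.6.
4. State which dose scheme receives an event with no start date.
5. Editorial: 7.2.8 uses a Week 8 visit as the floor for imputed follow-up onset dates. No such visit is in SAP Table 2; replace it with the D7 (FU1) visit. It affects relative days only.

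The cost is a few sentences in 7.2.6 and 7.2.8 and the matching program lines. The AE start times are already in the eCRF.

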7.2.7 Primary and Secondary Tolerability Endpoints

*A global ocular discomfort score will be assessed by the subject using a self-administered 100 mm visual analogue scale (VAS) on which 0 means no symptoms and 100 means the worst possible discomfort. This evaluation is to be performed **before** any ophthalmic assessment at a given study visit.*

The VAS Ocular tolerability scores will be collected on the eCRF page “Visual Analogue Scale Ocular Tolerability” per eye for the symptoms:

- Foreign body sensation
- Burning/stinging
- Itching
- Ocular pain
- Sticky feeling
- Blurred vision
- Photophobia

The assessments should be performed at Baseline Visit 0hr, D1 8hr, D2 Pre-Dose, D2 8hr, D3 Pre-Dose, D6 Pre-Dose, D6 8hr, FU1 0hr, FU2 8hr, Fu3 0hr.

The Overall VAS Ocular Tolerability Score acts as a global discomfort score and is defined as the mean of all VAS Ocular Tolerability symptom scores per visit per eye. In case of missing symptom scores, the mean will be calculated on the remaining VAS scores if at least 5 out of 7 scores are non-missing.

The primary tolerability endpoints for the assessment of the single dose scheme are defined as Change from Baseline of the D2 Pre-Dose value in the study eye. Baseline is defined as the corresponding assessment at Baseline Visit 0hr. This will be derived for the Overall VAS Ocular Tolerability Score as well as for each single symptom scale.

The primary tolerability endpoints for the assessment of the multiple dose scheme are defined as Change from Multiple Dose Baseline, i.e. the difference between the considered VAS score in the study eye at D2 8hr, D3 Pre-Dose, D6 Pre-Dose, D6 8hr, FU1 0hr, FU2 8hr, Fu3 0hr and the D2 Pre-Dose value in the study eye. This will be derived for the Overall VAS Ocular Tolerability Score as well as for each single symptom scale.

Secondary tolerability endpoints are:

- the raw VAS ocular tolerability scores in Study Eye and Non-Study Eye at all scheduled visits.
- the intra-individual differences in VAS ocular tolerability scores between Study Eye and Non-Study Eye at all study visits.

7.2.8 Secondary Safety Endpoints – Adverse Events

General Definitions

AE data are collected on the “Adverse Events” eCRF page. The AE Description (Investigator term) will be analyzed on PT and SOC level using MedDRA.

Based on the information provided on the “Adverse Events” eCRF page, the following definitions will be utilized:

- An ocular event will be identified, if the question “Is this an ocular event?” is answered ‘Yes’.
- An AE with missing severity will be counted as severe.
- A Serious Adverse Event (SAE) is any adverse event where the question “Is the event serious?” has been answered as ‘Yes’. If this question is not answered the event will be considered as ‘Serious’ for analysis purposes.
- *For this study medically important events comprise the following sight threatening events, which are considered to be of special interest (AESI) and by default are to be reported as SAEs:*
 - *Adverse Events that caused a decrease in visual acuity of >30 ETDRS letters or > +0.6 LogMAR (compared with the last assessment of visual acuity at the last visit) lasting >1 hour*
 - *Adverse Events that cause a decrease in visual acuity to the level of Light Perception or worse lasting >1 hour*
 - *Adverse Events that require surgical intervention (e.g., conventional surgery, vitreous tap or biopsy with intravitreal injection of anti-infectives, or laser or retinal cryopexy with gas) to prevent permanent loss of sight*
 - *Adverse Events associated with severe intraocular inflammation (i.e., 4+ anterior chamber cell/flare or 4+ vitritis)*
 - *Adverse Events that, in the opinion of the investigator, may require medical intervention to prevent permanent loss of sight.*

For analysis purposes, AESI will be identified as all ocular event, with a ticked box ‘Medically significant or important medical condition’ in the eCRF section “SAE criteria”.

This definition will be verified during the BDRM.

- An AE leading to premature withdrawal of the study treatment is defined as an AE where in the eCRF section “Action taken with study treatment” the boxes ‘Withdrawn’ and ‘Permanently’ are ticked.
- An AE leading to study treatment interruption is defined as an AE where in the eCRF section “Action taken with study treatment” the boxes ‘Withdrawn’ and ‘Temporarily’ are ticked.
- An AE leading to study discontinuation is defined as an AE where in the eCRF section “Action regarding Subject” the box ‘Subject Withdrawn’ is ticked.
- An AE is classified as ‘Related’ to Study Treatment if the relationship to study medication recorded as ‘Possible’ or ‘Probable’ or ‘Highly Probable’. An AE will be classified as unrelated to study medication if the relationship to study medication was recorded as ‘None’ or ‘Unlikely’. AEs with missing relationship to study treatment will be counted as ‘Related’ to Study Treatment.
- A Fatal AE is defined as an AE where the outcome is recorded as ‘Fatal’.

These definitions will apply accordingly also for the subsequent sub-classes of AEs.

Non Treatment-emergent adverse events (Non-TEAEs)

A Non-TEAE is defined as any AE, which started before the first administration of study treatment. An AE is considered as Non-TEAE, if the eCRF question “Did the event occur:” was answered with ‘Before Treatment Period’.

Treatment-emergent adverse events (TEAEs)

A treatment-emergent adverse event is defined as an AE that started on or after the date of the First Study Treatment Administration. An AE is considered as TEAE, if the eCRF question “Did the event occurred:” was answered either with ‘During Treatment Period’ or ‘During Follow-Up Period’.

TEAEs in Treatment Period

This is defined as a TEAE (as defined above) that started on or after the date of the First Study Treatment but on or before the D6 Visit. A TEAE in Treatment Period will be identified, if the eCRF question “Did the event occurred:” was answered with ‘During Treatment Period’.

TEAEs in Follow-Up Period (FUAE)

This is defined as a TEAE with a start date on or after D7 Visit. A TEAE will be considered as TEAE in Follow-Up Period, if eCRF question “Did the event occur:” was answered with ‘During Follow-Up Period’.

For listing purposes, treatment day of onset of AE will be derived according to the definition given in section 7.1.

Missing Codes or Incomplete AE start dates:

In the event that coding information will not be available for a specific AE, the event will be presented as ‘Uncoded Event’. However, for final TLFs it is anticipated that all events are coded.

If the eCRF question “Did the event occur:” was not answered, AEs will be classified to subclass Non-TEAE, TEAE in Treatment Period or In Follow-Up Period based on the AE onset date utilizing the definitions given above. If this is not possible, the event will be classified as TEAE in Treatment Period.

Missing and/or incomplete AE onset dates will be imputed for calculating relative start and stop days only. Dates will be listed as missing/incomplete [with “-” replacing missing information] but the onset Day listed between square brackets to denote it was calculated based on missing data (i.e. [1]).

Missing and/or incomplete dates will be imputed in a manner that assumes the worst case scenario:

- For a missing start day (but month and year is available), onset is assumed on the first day of the respective month.
- For a missing start month (but year is available), onset is assumed on 1st January of the respective year.
- For a completely missing start date, no imputation will be performed.

If for Non-TEAEs this procedure results in an onset date before date of informed consent, informed consent date will be used.

If for TEAEs in the Treatment Period this procedure results in an onset date before date of first study treatment, date of first study treatment will be used.

If for TEAEs in the Follow-Up Period this procedure results in an onset date before date of Week 8 visit, date of Week 8 visit will be used.

Secondary Safety Endpoints

The incidence of FUAEs as well as the Incidence of ocular TEAEs occurring in study eye and non-study eye will serve as secondary study endpoints following the definitions specified above.

